5.2 Treatment arms

Following protocol Amendment 6 patients will be assigned to one of the following 4 treatment arms in a ratio of 1.4 : 1.3 : 1.3 : 2

- Canakinumab 50 mg s.c. at randomization (month 0), placebo s.c. at week 2 (month 0.5) , 50 mg s.c. at week 12 (month 3) and thereafter 50 mg s.c. quarterly
- Canakinumab 150 mg s.c. at randomization (month 0), placebo s.c. at week 2 (month 0.5), 150 mg s.c. at week 12 (month 3) and thereafter 150 mg s.c. quarterly
- Canakinumab 300 mg s.c. at randomization (month 0), week 2 (month 0.5) , week 12 (month 3) and thereafter 300 mg s.c. quarterly
- Placebo s.c. at randomization (month 0), week 2 (month 0.5) , week 12 (month 3) and thereafter placebo s.c. quarterly

with allocation in a 1.3 : 0.7 : 1 ratio to 300 mg, 150 mg and placebo respectively in randomization plan A and 0.6 : 1.4 : 1 to 150 mg, 50 mg and placebo respectively in randomization plan B. All patients will be equally likely to be assigned to randomization plan A or B. Within each of the two randomization plans patients will have a 2:1 probability of being on active treatment. Prior to protocol amendment 6, patients were assigned in a 1:1:1

ratio to the 300 mg arm, the 150 mg arm or placebo. Across trial parts 1 and 2 this will approximately result in a 1:1:1:1.5 allocation to 300, 150, 50 mg and placebo, respectively. More precisely, given about 743 patients in trial part one and 9257 in trial part 2, the overall patient allocation would be approximately 2253 for both the 300 and 150 mg groups, 2160 for the 50 mg group and 3333 for the placebo group (a 1.01:1.01:0.97:1.5 ratio).

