## **2.4 Key trial design aspects relevant to trial analysis**

### **Randomization and blinding**

Initially, patients were randomized in a 1:1:1 fashion to 300 mg canakinumab with induction dose, 150 mg without an induction dose or placebo quarterly. Following Health Authority feedback on the doses a lower 50 mg dose arm was added in protocol amendment 6 in order to

examine the dose response of canakinumab in preventing recurrent cardiovascular events, and to determine if a dose lower than 150 mg would have a favorable risk benefit ratio. Following this amendment, randomized allocation to the four trial arms was to be unbalanced in order to optimize power, now that three active arms were compared versus a common control arm.

**Figure 2-3 Patient allocation to treatment arms prior and after protocol amendment 6 including reduced patient numbers following protocol amendment 8**

Protocol amendment 6 introduced 50 mg dose. In protocol amendment 8, the total sample size was changed from 17,200 to 10,000. The allocation to active drug is always 2:1 (in Part I, Part IIA and IIB).

Prior to protocol amendment 6, the following two presentations of canakinumab solution for injection in pre-filled syringes are used in CANTOS:

- Canakinumab 150 mg/1 ml, and
- Placebo matching canakinumab 150 mg/1 ml

In addition, the following pre-filled syringes were available to be used for the purpose of implementing the 50 mg arm following amendment 6:

- Canakinumab 50 mg/0.5 ml, and
- Placebo matching canakinumab 50 mg/0.5 ml.

Canakinumab 50 mg/1 ml pre-filled syringes that fully match 150 mg pre-filled syringes were not available near the time of protocol amendment 6. Thus, in order to evaluate 300 mg, 150 mg and 50 mg versus placebo in a fully blinded fashion, a triple-dummy design with 3 injections per visit would have been required. As feedback from investigators indicated that this would constitute an unacceptable burden to patients we identified the approach shown in [Figure 2-3](#) as the most appropriate solution for introducing the 50 mg dose into the CANTOS trial.

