Note that no assumption of proportional hazards is necessary to test whether there is a higher probability of MACE in canakinumab than on placebo, because the employed stratified log-rank tests are valid even without proportional hazards. This assumption is only necessary to calculate estimated hazard ratios with confidence intervals for the effect of treatment ([Bland and Altman 2004](#)).

The family-wise error rate will be controlled at the two interim analyses and the final analysis using the closed testing procedure shown in [Figure 6-4](#) based on the graphical method of Bretz et al. ([Bretz, et al 2009](#)); however, in intersection null hypotheses involving the primary null hypotheses for the 300 mg, 150 mg or 50 mg doses these primary null hypotheses will be tested using a weighted version of Dunnett's test ([Dunnett 1955](#)). Specifically this means that for any intersection hypothesis from the full closure that contains at least two of  $H_{11}$ ,  $H_{21}$  and  $H_{31}$ , a weighted Dunnett test amongst the primary null hypotheses is performed with the overall significance level for that test and the weighting chosen according to the weights assigned to these null hypotheses by the update algorithm of the graphical method. The nominal adjusted significance levels based on the weighted Dunnett test are always slightly larger than the corresponding Bonferroni levels would be. For example the `mvtnorm` package in R ([Genz and Bretz 2009](#)) calculates the nominal Dunnett significance levels at the final

analysis for the 300 mg, 150 mg and 50 mg doses versus placebo adjusting for the interim analysis in the test of the global null hypothesis to be 0.5500504%, 1.1001008% and 1.1001008%, respectively, as compared to Bonferroni levels of 0.49%, 0.98% and 0.98%. If other non-primary null hypotheses in such an intersection hypothesis have non-zero weight on the basis of Figure 6-4, the intersection null hypothesis will be rejected if either (a) these other null hypotheses can be rejected at a Bonferroni significance level based on that weight or (b) the primary null hypotheses can be rejected based on the weighted Dunnett test.

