Two efficacy interim analyses, at which the trial could be stopped for demonstrated efficacy, or one or more active arms could be stopped for futility, will be performed respectively after

50% and 75% of the target number of 1,400 patients have experienced a primary endpoint. Futility criteria and the criteria other than purely formal statistical significance required for stopping the trial for demonstrated efficacy will be specified in the Data Monitoring Committee charter. Protocol amendment 8 introduced an additional early futility analysis to be performed at approximately 30% of the target number of 1400 patients have experienced CEC confirmed MACE. The analysis plan of the early futility was discussed in a separate document.

A fixed Bonferroni split of the one sided significance level will be used to account for the two efficacy interim analyses and the final analysis, with a significance level of 0.01% for the first and 0.04% for the second efficacy interim analysis. I.e. the closed testing procedure will be performed with an one-sided significance level of 0.01% at the first efficacy interim analysis, with an one-sided significance level of 0.04% at the second efficacy interim analysis and with an one-sided significance level of 2.45% at the final analysis. In this fashion the familywise type I error rate will be controlled at the overall (one-sided) significance level  $\alpha = 2.5\%$ .

No multiplicity adjustment will be made for the additional early futility analysis, because it will not result in rejecting a null hypothesis for efficacy superiority.

The appropriate nominal weighted Dunnett significance levels will be calculated e.g. using the mvtnorm R package ([Genz and Bretz 2009](#)). For the example of the global null hypothesis this can be done using R code (or corresponding SAS code) similar to the following

```
library(mvtnorm)
alpha <- 0.0245 # level at which Dunnett test is performed
rho <- 0.5 # assumed correlation of test statistics
corr <- (1-rho)*diag(3)+rho # correlation matrix
weight <- c(0.2,0.4,0.4) # weights for hypotheses in Dunnett test
alphaw <- alpha*weight
MVN <- function(alpha1, w, corr, alpha){
  x<-qnorm(1-alpha1*w)
  return(1-pmvnorm(upper=x,corr=corr) - alpha)
}
opt3 <- uniroot(MVN, lower = alpha, upper = 2*alpha, w=weight,
corr=corr, alpha=alpha, tol=1E-12)
critwDun <- qnorm(1-opt3$root*weight)
nominal <- opt3$root*weight
```

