### Calculation of multiplicity adjusted one- and two-sided p-values

Multiplicity adjusted p-values will be calculated for each null hypothesis as the smallest significance level at which one can reject that null hypothesis using the testing procedure shown in [Figure 6-4](#) while also taking into account the interim analyses. For this purpose the algorithm described by [Bretz et al. \(2009\)](#) will be applied to the unadjusted one-sided p-values and the resultant p-values (adjusted only for the multiple endpoints and doses) will be adjusted for the interim analyses by scaling them by a factor of 250 (=0.025/0.0001) at the first efficacy interim analysis, 62.5 (=0.025/0.0004) at the second efficacy interim analysis and 0.025/0.0245 ( $\approx 1.02$ ) at the final analysis. Because a weighted Dunnett test will be used for any intersection hypothesis from the full closure that contains at least two of  $H_{11}$ ,  $H_{21}$  or  $H_{31}$ , the algorithm of [Bretz et al. \(2009\)](#) needs to be extended. For this purpose the weights  $w_{11}$ ,  $w_{21}$  and  $w_{31}$  used as part of that algorithm would be defined as the respective Dunnett level divided by the overall significance level at the respective analysis.

For example, for the global null hypothesis instead of  $w_{11}=0.2$ ,  $w_{21}=0.4$  and  $w_{31}=0.4$  as for a Bonferroni test based procedure – for which  $w_{11} + w_{21} + w_{31} \leq 1$  would always hold – instead  $w_{11} + w_{21} + w_{31} > 1$  would hold in this case. For example, using the nominal Dunnett significance levels for 300 mg, 150 mg and 50 mg doses at the final analysis calculated using the mvtnorm package in R as described earlier in [section 6.3.1](#), one obtains  $w_{11} = 0.5500504\% / 2.45\% \approx 0.2245103$ ,  $w_{21} = 1.1001008\% / 2.45\% \approx 0.4490207$  and  $w_{31} = 1.1001008\% / 2.45\% \approx 0.4490207$ .

In case health authorities, journals or the data monitoring committee require two-sided p-values, these will be provided in a manner that firstly ensures that the test decision on the rejection of the primary and key secondary null hypotheses remains unchanged and that secondly uses in principle the same testing procedure for evaluating the potential superiority of placebo over each dose of the test drug.

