The overall aggregated cohort survival estimate will be obtained from the estimates for each treatment group / time since index MI / trial part combination using the Hakulinen method ([Hakulinen 1982](#)). Compared with the more simple Ederer method this is expected to more closely reflect what might have been obtained, if this study had been conducted with 4 treatment arms from the start. The reason is that the follow-up time after which administrative censoring at trial end will occur will differ – by design – between the trial parts ([Thomsen et al. 1992](#)) ([Therneau and Grambsch 2000, pp. 261-287](#)).

The cohort for which the cumulative failure rate is estimated using the Hakulinen method will be constructed so that within each trial part the distribution of time since index MI and distribution of maximal potential follow-up is the same for each treatment group. To achieve this within each trial part

1. All the patients in all treatment groups and time since index MI strata in that trial part are selected.
2. Their length of follow-up  $F_i$  and time since index MI information is retained.
3. These patients are assumed to be the (identical) hypothetical recruited cohorts for each of the four treatment groups.

Note that the length of follow-up  $F_i$  is taken to be

- for those patients that were censored: the time from randomization to the maximum actual follow-up for CV events (not just for the first event)
- for patients that had a non-fatal version of the endpoint of interest (e.g. non-fatal MI in case of analyzing the primary MACE endpoint) the same approach as for those patients that were censored will be used
- for patients that had a fatal version of the endpoint of interest (e.g. fatal MI in case of analyzing the primary MACE endpoint) the maximum potential follow-up will be used, i.e. the time from randomization to the maximal potential follow-up date, defined to be the analysis cut-off date (see [Section 2.3.7](#)).

For each patient  $i$  let  $S_i(t)$  be the estimated survival curve based on that patient's treatment group, time since index MI and trial part. If patients are ordered from shortest to longest possible follow-up time  $F_{(1)}, F_{(2)}, \dots, F_{(k)}$ , then the Hakulinen estimate ([Hakulinen 1982](#)) for the cumulative survival function  $S(t)$  is calculated recursively for any  $F_{(k)} < t \leq F_{(k+1)}$  as

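### The example Dunnett levels assume a correlation of 0.5; the planned allocation gives about 0.37 to 0.41, so the printed levels spend about 2.55% at the final look instead of 2.45%

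*SAP*

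**What the plan says.** SAP 6.3.1 tests the primary hypotheses H11 (300 mg), H21 (150 mg) and H31 (50 mg) with a weighted Dunnett test in every intersection that contains at least two of them. The initial weights are 0.2, 0.4 and 0.4. Its R code sets "alpha <- 0.0245 # level at which Dunnett test is performed" and "rho <- 0.5 # assumed correlation of test statistics", with one correlation for all three pairs. SAP 6.3.1 and Protocol 9.4.2 both print the levels "in the test of the global null hypothesis to be 0.5500504%, 1.1001008% and 1.1001008%, respectively" for 300, 150 and 50 mg. The SAP subsection on multiplicity-adjusted p-values then builds its weights "using the nominal Dunnett significance levels for 300 mg, 150 mg and 50 mg doses at the final analysis calculated using the mvtnorm package".

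On error control SAP 6.3.1 states: "In this fashion the familywise type I error rate will be controlled at the overall (one-sided) significance level" of 2.5%, with 0.01% and 0.04% at the two efficacy interims and 2.45% at the end.

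On arm sizes, SAP 2.4 says that after protocol amendment 6 "randomized allocation to the four trial arms was to be unbalanced in order to optimize power". Protocol 5.2 expects "approximately 2253 for both the 300 and 150 mg groups, 2160 for the 50 mg group and 3333 for the placebo group". Part 1 was randomized 1:1:1 without a 50 mg arm, and the log-rank test is stratified by trial part.

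**The concern.** Two dose-versus-placebo statistics are correlated because they share the placebo arm. With unstratified arms of size n_i, n_j and n_0, the null correlation is sqrt[n_i/(n_i+n_0)] × sqrt[n_j/(n_j+n_0)]. All three pairs reach 0.5 only if every dose arm equals placebo. A larger placebo arm lowers the correlation. A dose that is absent from part 1 shares less placebo information with the others, which lowers it again.

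A lower true correlation means less overlap between the three rejection events. Levels tuned to 0.5 then reject too often. Family-wise control at one-sided 2.5% is the trial's confirmatory claim, and the error runs in the direction of a positive result.

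**Working it through.** **Inputs.** Printed levels, weights and 2.45%: SAP 6.3.1. Part sizes of 743 and 9257: Protocol 5.2. Part 2 allocation 2 : 1.4 : 1.3 : 1.3 (placebo, 50, 150, 300 mg): Protocol synopsis, sample size. Assumption: under the null, events are proportional to planned patients by arm and part.

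**Step 1, the plan's own figure.** Solving P(any Z_i > z(1 − c·w_i)) = 2.45% at a common correlation of 0.5 gives 0.5498/1.0996/1.0996%. The printed levels spend 2.451% there, so they reproduce.

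**Step 2, unstratified check.** At 1:1:1:1.5 the correlation is 1/2.5 = 0.40, and the printed levels spend 2.546%.

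**Step 3, correlations stratified by part.** With π_i = e_i/(e_i + e_P) in each part, V_i = Σ e_P·π_i and Cov_ij = Σ e_P·π_i·π_j.

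- Part 1: e_P = 743/3 = 247.7; π = 0.5 for 300 and 150 mg.
- Part 2: e_P = 9257 × 2/6 = 3085.7; π = 1.3/3.3 = 0.3939 for 300 and 150 mg, and 1.4/3.4 = 0.4118 for 50 mg.
- V(300) = V(150) = 123.8 + 1215.6 = 1339.4; V(50) = 1270.6.
- Cov(300,150) = 61.9 + 478.9 = 540.8, so the correlation is 540.8/1339.4 = 0.404.
- Cov(300,50) = Cov(150,50) = 500.5, so the correlation is 500.5/√(1339.4 × 1270.6) = 0.384.

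**Step 4, error at the printed levels, final look, global null.** All initial weight sits on the three primary hypotheses, so this is the family-wise error under the global null. SAP 6.4.1 notes that "the follow-up time after which administrative censoring at trial end will occur will differ" between the parts, but the documents give no events per patient by part. I therefore let a part 1 patient contribute m times the events of a part 2 patient.

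| m | 300/150 | pairs with 50 mg | error at printed levels | levels that spend 2.45% |
|---|---|---|---|---|
| 1 | 0.404 | 0.384 | 2.554% | 0.527/1.054/1.054% |
| 1.25 | 0.406 | 0.379 | 2.556% | 0.526/1.053/1.053% |
| 2 | 0.412 | 0.367 | 2.562% | 0.525/1.051/1.051% |

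If the tests are instead taken from a joint four-arm stratified model that uses the indirect part 1 information, the correlations are 0.405/0.390/0.390 and the error is 2.550% (m = 1). For a common correlation, the printed levels pass 2.5% at any value below about 0.45.

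**Step 5, all three looks.** Simulation at information fractions 0.5, 0.75 and 1 (40 million trials, standard error 0.0025 points) gives 2.556% for m = 1 and 2.561% for m = 2, against the claimed maximum of 2.5%.

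**Step 6, one further intersection.** Removing H11 alone passes 45% and 25% of its weight to 150 and 50 mg: 0.40 + 0.20 × 0.45 = 0.49 and 0.40 + 0.20 × 0.25 = 0.45. The Dunnett component should spend 0.94 × 2.45% = 2.303%. Levels set at 0.5 spend 2.366% (m = 1). This is the Dunnett component only; the key secondary hypotheses for 300 mg carry the rest of that intersection's alpha.

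**Step 7, alternatives.** The weighted Bonferroni levels already printed (0.49/0.98/0.98%) spend 2.285%. Approximate power at hazard ratio 0.8 and 1,400 events, for a single comparison at the global-null level, is as follows.

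| Dose | Printed | Corrected | Bonferroni |
|---|---|---|---|
| 300 mg | 72.9% | 72.4% | 71.6% |
| 150 mg | 80.6% | 80.1% | 79.4% |
| 50 mg | 79.6% | 79.1% | 78.3% |

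**The case against.** The strongest reply is that the SAP does not commit to 0.5. The code is introduced as an example, the value is labelled as assumed, and the text promises appropriate levels. An analyst who used the design-based correlation would comply with the plan. That is a fair reading, and it means the final analysis need not go wrong. But 0.5 is the only correlation in either document. Its output is printed as nominal levels in both and reused for the adjusted p-values. Protocol 9.4.2 shows the levels without the assumption behind them. Following the text as it stands gives thresholds that are slightly too generous.

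The second reply is size, and it stands. The excess is a few hundredths of a point over 2.5%. The observed risk reduction needed for 150 mg moves by only about 0.1 percentage point, well inside the 15 to 16% range in Protocol 9.6.

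The power figures above are single comparisons and do not match Table 9-1, which reports the closed procedure. Each table entry rests on 5,000 simulations, so at 80.3% its standard error is √(0.803 × 0.197/5000) = 0.56 points. A half-point loss lies within that noise.

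**Conclusion.** The concern holds. The printed levels are right for a correlation of 0.5 and wrong for this design. At the planned allocation they spend 2.55 to 2.56% at the final look and about 2.56% over all looks, against stated limits of 2.45% and 2.5%. The 0.05% reserved for the interims cannot absorb this, because the final look alone exceeds 2.5%.

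The practical reach is narrow. In the global test it matters only for one-sided p-values between about 1.05% and 1.10% for 150 or 50 mg, or between 0.527% and 0.550% for 300 mg. The result assumes null events in proportion to planned patients. It changes little over the range of part 1 event yields tried, under a joint model, or when strata are ignored. It should be fixed because it contradicts a confirmatory claim and the fix is cheap.

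**What to change.** Before unblinding, add a rule to SAP 6.3.1: the correlation matrix is the one implied by stratum-specific allocation or by observed event counts by stratum, in place of 0.5. Recompute the levels for every intersection with two or more primary hypotheses at each look, and restate the global-null example (about 0.527/1.054/1.054% at the final look). Use the same matrix for the multiplicity-adjusted p-values, evaluating the multivariate normal probability directly. Correct the example in Protocol 9.4.2 to match. The weighted Bonferroni levels are a fallback that needs no correlation.

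The cost is a sentence or two, a few lines of code, and a written amendment under Protocol 11.1 for the protocol text. The nominal levels fall by about 4% in relative terms, which costs about half a point of power per dose; Bonferroni would cost 1.2 to 1.3 points. Rerunning the 20% row of Table 9-1 is optional but sensible, since 50 mg stands at 80.3% against an aim of at least 80%.

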### **Supportive, sensitivity and subgroup analyses for the primary endpoint**

The components of the composite primary efficacy endpoint (CV death, fatal or non-fatal MI, fatal or non-fatal stroke) will also be analyzed individually in order to evaluate their contributions to the overall treatment effect. No adjustment for multiplicity is foreseen for this purpose.

The three pooled canakinumab doses will be compared to placebo on the primary composite endpoint and its components, because in case of similar efficacy on all three doses this would be the most powerful test of the scientific hypothesis addressed by this trial. Additionally, when all three doses have similar efficacy, such a pooled analysis approach may provide the most precise information on the effects in subgroups.

Dose response will be evaluated using the methods discussed in [section 6.5](#). Additionally, comparisons between the canakinumab doses based on the primary model will also be reported.

Kaplan-Meier type analyses will be presented as described in [section 6.4](#) overall and by trial part to summarize the time to first event in the composite endpoint, by presenting the time-dependent cumulative frequency and percentage of patients who reach the primary composite endpoint by treatment group.

Additionally, log time by treatment interaction will be evaluated to identify violations in the proportional hazards assumption, which might indicate a time-varying treatment effect. An Anderson-Darling type test based on a score process (cumulative sum of the Schoenfeld residuals) as recommended by Kvaløy and Neef ([Kvaløy and Neef 2004](#)) will be performed. For each trial arm within each trial part  $-\log(S(\text{time}))$  vs. time and  $\log(-\log(S(\text{time})))$  vs.  $\log(\text{time})$  will be plotted.

To ensure that any unblinding of patients during the double-blind phase had no meaningful impact on the overall study results, a sensitivity analysis of the primary endpoint will be performed by excluding data from all patients who were unblinded during the double blind phase of the study (i.e. all the unblinded patients will be censored at the time of unblinding).

The primary variable and its components will also be analyzed on the PPS1. Additionally, in an on-treatment analysis on the FAS, patients will be considered censored at the latest 28 days after the end of the double-blind treatment phase, which corresponds to up to 119 days after the last study drug injection based on the long elimination half-life of the drug. 91 days constitute a bit over 3 half-lives and 28 days add an additional half-life. In the on-treatment analysis patients will stay in the risk set until this point unless their censoring date occurred earlier and will not leave and re-enter the risk set due to treatment interruptions. Besides adjudicated endpoints investigator reported outcomes will also be analyzed on the FAS.

Once the results become available a covariate adjusted analysis may be considered. This covariate-adjusted Cox-regression model will consider the following pre-specified baseline covariates: linear age, sex, race, linear BMI, smoking status, region as defined in [section 2.2](#), linear baseline log hsCRP, type of qualifying MI (STEMI/NSTEMI/Unknown), glycemic status, duration of diabetes for diabetic patients, hypertension, linear baseline systolic blood pressure, linear and quadratic baseline diastolic blood pressure, history of heart failure, dyslipidemia, linear baseline LDL-C, linear baseline HDL-C, linear baseline triglycerides, linear number of prior MIs, prior PCI, prior TIA/stroke, linear eGFR, no/low or medium dose/high dose statin use at baseline as defined in [section 5](#), baseline aspirin therapy, baseline P2Y12 therapy, RAAS inhibitor use, beta blocker use, to account for other factors that might affect prognosis.

Furthermore, the pre-specified subgroup analyses will be conducted for the subgroups listed in [section 2.2](#). Results will be presented graphically as forest plots. The objective of the subgroup analyses is to evaluate the consistency of treatment effects across a wide variety of patient groups. For this purpose the availability of data from three different doses should be helpful, because most subgroup effects would be affect all doses to some extent, which provides an additional way of identifying spurious findings that occurred by chance. Additional subgroup analyses will be considered and potentially pre-specified prior to unblinding of trial database for final analysis. It is clear that due to the number of subgroups a substantial number of totally spurious numerical imbalances in treatment effects between subgroups has to be expected – including some with an interaction p-value  $\leq 0.05$  and/or with apparently no or reversed effects. [The association between changes in hsCRP and outcomes will also be explored.](#)

To assess whether pooling randomization plan A and B in trial part 2 is appropriate, the placebo groups in randomization plans A and B will be compared against each other, the 150 mg groups in randomization plan A and B will be compared and the 150 mg versus placebo contrasts will be compared qualitatively between randomization plan A and B.

As a further sensitivity analysis in this respect, randomization plan will be used as an additional stratification factor in the primary model. This analysis will use SAS code similar to the following (where randomization plan would be a 3 level stratification factor with 1 level for trial part 1 and two further levels for each randomization plan in trial part 2) or equivalent code in another programming language such as R :

```
proc phreg data=dataset;  
  class treatment(ref="Placebo") <time since index MI>  
  <randomization plan>;
```

```
model time*event(0) = treatment treatment*<randomization plan>
  / ties=exact risklimits;
strata <time since index MI> <randomization plan>;
hazardratio treatment / diff=ref cl=both;
run;
```

A sensitivity analysis with respect to the consistency of treatment effects in the two parts of the trial will also be performed. This analysis will use SAS code similar to the following or equivalent code in another programming language such as R:

```
proc phreg data=dataset;
  class treatment(ref="Placebo") <time since index MI> <trial part>;
  model time*event(0) = treatment treatment*<trial part>
    / ties=exact risklimits;
  strata <time since index MI> <trial part>;
  hazardratio treatment / diff=ref cl=both;
run;
```

